6.4.2. Primary Safety Endpoint

The primary safety endpoint is a composite of major complications associated with the procedure or study device and defined as complications resulting in an unplanned increase in the level of care, prolonged hospitalization, permanent adverse sequelae, or death.¹⁰

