ICE uses a low-frequency, side-firing intravascular transducer and is more commonly used for intracardiac procedures. However, in this application it can be used to depict the central portion of the liver, which permits visualization of the needle and the PV target without the use of fluoroscopy or contrast medium.

Cam et al.⁴ reported that ultrasound-guided PV access and percutaneous PV guidewire placement for fluoroscopic targeting during TIPS creation are associated with shorter procedure and fluoroscopic times and potentially decreased complications. Many of the procedure-related complications of TIPS creation, such as arterial injury, biliary injury, and extracapsular puncture may occur during attempted portal vein access. As the number of needle passes for successful PV access increases, so may the potential for puncture-related complications.

Historically, the most performed technique for portal venous access involved wedge hepatic venography with carbon dioxide to visualize the portal vein followed by passing the needle under fluoroscopic guidance. In the last 10 years, imaging guidance options have evolved beyond traditional wedge carbon dioxide portography to include ultrasound-guided options such as transabdominal, intravascular and intracardiac echocardiography to help with visualization and portal vein cannulation. Portal vein access may require multiple needle passes and is considered the riskiest step in TIPS creation with possible incidence of portal vein puncture-related complications (PVPC).⁵ Complications result from inadvertent injury to non-target vessels and include damage to the hepatic artery or extrahepatic portal vein, transcapsular puncture and laceration of the liver capsule, all of which can result in life-threatening hemorrhage.⁶

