3.2. Prior Investigations

The Rosch-Uchida and Colapinto sets manufactured by Cook Medical (Bloomington, Indiana, US) are two different needle sets currently available and most encountered. A recent systematic review of literature showed that the overall incidence of PVPC with the Cook sets was 3.6%.⁶ The procedure duration varies in literature due to protocol differences and imaging techniques used. David et al.⁷ reported a mean procedure duration of 86.2 minutes using ultrasound guidance. In a study evaluating time to portal vein access, mean time to portal venous access was statistically significant between conventional fluoroscopy at 46 minutes and intravascular US-guided TIPS at 31 minutes.⁸

In the paucity of studies available which focus on portal vein access in TIPS interventions, there are few that demonstrate significant differences between the number of needle passes. The data is incomplete because fewer than half of conventional TIPS cases in literature included a recording of the actual number of passes. The Scorpion devices allow for bi-directional positioning of the needle or stylet for precise placement during portal vein puncture.

In a retrospective study of 15 cases with Scorpion X (Needle model), technical success was achieved in 100% of cases with an average of 2.7 passes, and because of the bi-directional needle, no cases required adjustment to the curvature of the needle.⁹

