5. RISK/BENEFIT ANALYSIS

5.1. Potential Clinical Benefits

The study devices facilitate transjugular liver access and portal vein access in TIPS procedures.

The design of the Scorpion set should improve the physician's ability to navigate through the liver parenchyma and reduce the number of attempts necessary to establish access to the portal vein, particularly in diseased livers where irregular anatomy is frequently observed. There are no guaranteed benefits from participation in this study; however, potential clinical benefits may include:

- Shorter procedure duration
- Shorter fluoroscopic times
- Improved navigation control
- Reduced needle passes for successful PV access
- Decreased puncture-related complications

Information gained from the conduct of this study may be a benefit to physicians and other persons with the same medical condition.

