6.4.3. Secondary and Exploratory Endpoints

The secondary and exploratory endpoints of this clinical study are outlined in **Table 5**.

TABLE 5. OVERVIEW OF SECONDARY AND EXPLORATORY ENDPOINTS

Endpoint	Description / Definition
Secondary Endpoints	
Portal Vein Access (PVA) time	Time (in minutes) from initial needle throw to portal vein access as confirmed by portogram
Technical success	Creation of a shunt (stent bridging) between the portal and systemic veins
Number of needle passes	Count of needle throws between the hepatic and portal vein to create the parenchymal tract
Procedure duration	Interval (in minutes) from first jugular access for TIPS creation to removal of catheters from subject
Fluoroscopy time	Measured in minutes
Device-related complications	Incidence of complications related to the device as judged by the Principal Investigator
Exploratory Endpoints	

Change in MELD score	Change in score from Screening to Day 30
Change in Child-Pugh score	
Radiation dosage	Measured in air kerma (mGy)
Contrast volume used	Measured in mL
Length of Hospital Stay	Measured in days
Number of ICU days	Measured in days
Change in HPVG	Measured in mm Hg

MELD = Model for End-Stage Liver Disease; ICU = Intensive Care Unit; HPVG = Hepatic Venous Pressure

Gradient

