10.4.1. Anticipated Adverse Events

The following adverse events may occur and are typically associated with the TIPS procedure:

² If an investigational device gives an incorrect diagnosis, the patient might, for example, receive an unnecessary treatment and incur all the risks that accompany that treatment, or might be incorrectly diagnosed with a serious disease. In other cases, the patient might not receive an effective treatment (thereby missing out on the benefits that treatment would confer) or might not be diagnosed with the correct disease or condition.

Hepatic encephalopathy
Infection/Sepsis
Liver failure
Contrast induced nephropathy
Allergic reaction to contrast utilized intra-procedurally
Adverse reactions associated with administration of general anesthesia or conscious sedation
Death

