10.4.2. Anticipated Adverse Device Effects

Adverse events related to the use of the Scorpion set or Cook Transjugular Liver Access set may include the following:

Intraperitoneal hemorrhage or hemoperitoneum
Puncture site hematoma
Cardiac arrhythmia
Cardiac tamponade
Arteriovenous fistula or other arterial injury
Arterio-biliary fistula or biliary tract injury
Extrahepatic Organ Injury
Capsular Perforation
Needle/catheter/guidewire fracture
Foreign body retention

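### No endpoint counts puncture-related complications, the protocol's key access risk; the primary composite dilutes them and the nearest secondary endpoint is only a partial proxy

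*Combined protocol and SAP*

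**What the plan says.** Section 6.4.2 defines the primary safety endpoint as "a composite of major complications associated with the procedure or study device", with major defined by consequence (higher level of care, longer stay, permanent sequelae, death) and not by mechanism.

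The protocol sorts expected events into two lists. Section 10.4.1 opens with "The following adverse events may occur and are typically associated with the TIPS procedure" and names encephalopathy, infection or sepsis, liver failure, contrast nephropathy, contrast allergy, anaesthesia reactions and death. Section 10.4.2 opens with "Adverse events related to the use of the Scorpion set or Cook Transjugular Liver Access set may include the following" and names, among others, haemoperitoneum, arterial injury, biliary injury, extrahepatic organ injury and capsular perforation. A major event from either list can enter the composite, and no split is planned.

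On puncture injury, section 3.1 ranks portal vein access as the riskiest part of the procedure and says the potential for puncture complications may rise with the number of needle passes. Section 3.2 reports that "the overall incidence of PVPC with the Cook sets was 3.6" per cent. Section 5.1 includes "Decreased puncture-related complications" among the potential benefits.

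The nearest endpoint is the secondary one in Table 5 (section 6.4.3): "Incidence of complications related to the device as judged by the Principal Investigator". The study is open-label (section 7.8). Section 11.3.3 bases device-specific post-operation safety on the primary effectiveness set, which section 11.3.2 limits to successful procedures that needed no alternative device.

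**The concern.** Of the five potential benefits in section 5.1, procedure duration, fluoroscopy time and needle passes each have an endpoint. The puncture-safety benefit has none by name. A reader of the final report would have to look for it in two places, and neither shows it cleanly. The primary composite adds events that the choice of access set affects less directly. The device-related endpoint depends on how an unblinded investigator assigns cause.

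The analysis set adds a possible bias. Treatment failures and crossovers are expected to have had at least five passes with the assigned set (sections 6.4.1 and 8.3). By section 3.1's own reasoning, puncture injury is more likely in these cases, yet they are the ones outside the set in section 11.3.2.

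The data are meant to support an initial CE mark application (sections 3 and 3.3). If the puncture count is assembled only afterwards from adverse event records, it is an unplanned analysis under section 11.6, with its terms chosen after open-label data have been seen.

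**Working it through.** **Inputs from the documents.** 30 subjects per group (synopsis, section 6.6); Cook PVPC rate 3.6% (section 3.2); Pearson chi-square for categorical outcomes (section 11.1.2). The sample size is declared empirical (section 11.2), with no alpha, power, margin or effect size, so there is no planned figure to reproduce.

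**Assumptions, none in the documents.** Two-sided 5% level and 80% power; PVPC halved from 3.6% to 1.8%; a non-puncture major-complication rate b, equal in both arms and independent of puncture injury, from 5% to 30%; every PVPC counts as major.

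**Step 1: dilution by the composite.** Composite rate = b + p − bp, where p is the PVPC rate. At b = 10%: 0.10 + 0.036 − 0.0036 = 13.2% against 0.10 + 0.018 − 0.0018 = 11.6%. The sample size per arm uses n = [1.96√(2p̄(1−p̄)) + 0.8416√(p₁(1−p₁) + p₂(1−p₂))]² / (p₁−p₂)², where p₁ and p₂ are the two arms' rates and p̄ is their mean.

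| b | Rate at PVPC 3.6% | Rate at PVPC 1.8% | Risk ratio | PVPC share at 3.6% | n per arm |
|---|---|---|---|---|---|
| 0 (PVPC alone) | 3.6% | 1.8% | 0.50 | 100% | 1,272 |
| 5% | 8.4% | 6.7% | 0.80 | 43% | 3,753 |
| 10% | 13.2% | 11.6% | 0.88 | 27% | 6,510 |
| 20% | 22.9% | 21.4% | 0.94 | 16% | 13,058 |
| 30% | 32.5% | 31.3% | 0.96 | 11% | 21,476 |

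PVPC share is 3.6% divided by the composite rate: the proportion of subjects with a composite event who have a puncture injury.

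**Step 2: the opposite direction.** Suppose PVPC tripled to 10.8%. On PVPC alone, the difference is 7.2 points, SE = √[(0.036×0.964 + 0.108×0.892)/30] = 6.6 points, and z = 1.09. On the composite, z is about 0.82 at b = 5%, 0.68 at 10% and 0.41 at 30%. The loss of effective sample size, 1 − (z/1.09)², is about 43%, 61% and 86%. Even the undiluted z is far below 1.96.

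**Step 3: what a PVPC endpoint could show with 30 per arm.**
- Expected events at 3.6%: 30 × 0.036 = 1.08 per arm.
- Probability of no event in an arm: 0.964³⁰ = 33.3%.
- Exact two-sided 95% upper limit for 0/30: 1 − 0.025^(1/30) = 11.6%. For 1/30 the interval is 0.1% to 17.2%.
- Power by exact enumeration of the Pearson test: 1.4% for 3.6% against 1.8%, and 6.5% for 3.6% against 7.2%.
- An arm with no events would need ln(0.025)/ln(0.964), or 101 subjects, for its two-sided 95% upper limit to reach 3.6%.

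**Step 4: which subjects are counted.** Section 11.3.1 assigns overall device safety to the intent-to-treat set (all attempted procedures). Section 11.3.3 assigns device-specific post-operation safety to the set of successes with the study device alone. The protocol does not say which applies to the secondary endpoint in Table 5. Follow-up also differs: section 6.4.1 has treatment failures followed through hospital discharge, while section 6.7 has enrolled subjects followed for 30 days.

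**The case against.** The plan is not silent on device safety. Device-related complications is a secondary endpoint, section 10.4.2 lists expected device effects by type, and section 10.5.1 asks for causality to device and/or procedure on each adverse event. Puncture injuries could be tabulated from those records, and injuries in failed cases still count in the overall safety assessment on the intent-to-treat set. The composite's definition comes from a cited guideline. This stands as a reason to keep the composite. It does not close the gap: section 10.4.2 also includes arrhythmia, device fracture and retained foreign body, attribution is unblinded, and a later tabulation would not be pre-specified.

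A reader might infer that the trial fails against its own 3.6% benchmark because of how the endpoint is built. The documents do not support that. Section 3.2 gives 3.6% as background, nothing is tested against it (sections 6.2 and 11.2), and step 3 shows that sample size is the binding limit.

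A reader might also infer that puncture injury is the only way the two sets could differ in safety. Section 5.1 allows for shorter procedure and fluoroscopy times, which could affect some procedure events indirectly, and section 10.4.2 lists device effects that are not puncture injuries.

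The size of the dilution is also open to challenge. The background rate is assumed, and section 7.3 excludes sicker patients, so the low end of the range must be shown.

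**Conclusion.** The point holds as a gap in pre-specification and interpretability. The protocol identifies puncture injury as the key risk of the access step and as a possible benefit of the device, but no endpoint isolates it. The primary composite would show a halving of PVPC as a risk ratio of 0.80 to 0.96 if the non-puncture rate is 5% to 30%, equal in both arms, and every PVPC is major. The secondary endpoint is a partial proxy whose analysis set is unclear and may leave out the cases at greater risk of puncture injury.

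It is not a claim about power. With or without a PVPC endpoint, 30 per arm can neither confirm nor exclude 3.6%. Nor can it be told from the documents whether the cited 3.6% covers all PVPC or only major ones, so a like-for-like comparison is not assured. This is a cheap improvement worth making, not a flaw that invalidates the primary safety result.

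**What to change.** Keep the primary composite and make these changes:

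- Add a secondary, descriptive endpoint of any PVPC, defined by event type: intraperitoneal haemorrhage or haemoperitoneum, arterial injury or fistula, biliary injury or fistula, extrahepatic organ injury and capsular perforation (from section 10.4.2), plus the extrahepatic portal vein injury named in section 3.1.
- Analyse it by randomised arm in all attempted procedures (section 11.3.1), not in the section 11.3.2 set. State which set applies to device-related complications.
- Report counts with exact confidence intervals by arm. State that 30 per arm cannot confirm or exclude 3.6%, and that the scope of the cited rate is unknown.
- Show the primary composite split into section 10.4.1 and section 10.4.2 event types.
- Reconcile sections 6.4.1 and 6.7 so that the observation window is the same for all subjects.

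The cost is one endpoint definition and one or two tables, largely from adverse event data already collected, plus one more exploratory comparison with very few events. One limitation remains: Table 6 schedules CT or MRI only at screening, so puncture injuries would still depend on detection and reporting by unblinded sites.

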6.4.3. Secondary and Exploratory Endpoints

The secondary and exploratory endpoints of this clinical study are outlined in **Table 5**.

TABLE 5. OVERVIEW OF SECONDARY AND EXPLORATORY ENDPOINTS

Endpoint	Description / Definition
Secondary Endpoints	
Portal Vein Access (PVA) time	Time (in minutes) from initial needle throw to portal vein access as confirmed by portogram
Technical success	Creation of a shunt (stent bridging) between the portal and systemic veins
Number of needle passes	Count of needle throws between the hepatic and portal vein to create the parenchymal tract
Procedure duration	Interval (in minutes) from first jugular access for TIPS creation to removal of catheters from subject
Fluoroscopy time	Measured in minutes
Device-related complications	Incidence of complications related to the device as judged by the Principal Investigator
Exploratory Endpoints	

Change in MELD score	Change in score from Screening to Day 30
Change in Child-Pugh score	
Radiation dosage	Measured in air kerma (mGy)
Contrast volume used	Measured in mL
Length of Hospital Stay	Measured in days
Number of ICU days	Measured in days
Change in HPVG	Measured in mm Hg

MELD = Model for End-Stage Liver Disease; ICU = Intensive Care Unit; HPVG = Hepatic Venous Pressure

Gradient

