1.3. Principal Investigator Contact Information

Each investigational site will have one physician designated as Principal Investigator (PI). Any other physicians involved in the study will be documented and referred to as a Sub-Investigator.

A current list of all investigational sites and Principal Investigators (including their roles, responsibilities, and qualifications) will be maintained separately from the protocol within the Trial Master File (TMF).

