7.4. Screening

Potential subjects will be identified from non-emergent cases scheduled for a TIPS procedure. All potential subjects will be contacted remotely or in-person by the treating physician (i.e., the PI) or

investigational site staff. During this contact, the PI will verify eligibility of the subject based on the inclusion and exclusion criteria listed in **Sections 7.2 and 7.3**.

Eligibility of potential subjects can be determined from historical laboratory, imaging, and echocardiography results previously taken per standard of care. Labs must have been taken within 30 days prior to the scheduled TIPS procedure. Imaging and echocardiography must have been obtained within 90 days prior to the scheduled TIPS procedure.

Subjects that fail to meet the study screening criteria will be documented as a screen failure on the study screening and enrollment log. Screen failures can be re-screened for study eligibility at the discretion of the Investigator. If a subject is re-screened, a new entry should be recorded on the study screening and enrollment log.

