7.8. Blinding

This is an open-label study. Blinding is not utilized.

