13.10. Minimization of Bias

The following activities are intended to reduce the risk of bias:

- Randomized study
- Objective methodology to evaluate endpoints
- Stratified randomization (if applicable after the interim analysis)

Furthermore, potential for bias has been minimized with a well-controlled design, expected conduct under the terms of the approved protocol, use of specific inclusion and exclusion criteria, careful definitions for study procedures and outcomes, and prospectively defined methods of data analysis.

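### Both safety endpoints depend on attribution to device or procedure in an open-label study with no independent assessor; an attribution-free count by arm should stand beside them

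*Combined protocol and SAP*

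**What the plan says.** Section 6.4.2 defines the primary safety endpoint as a "composite of major complications associated with the procedure or study device", with major defined by the consequence of the event. It names no assessor. Section 6.4.3 (Table 5) defines the secondary endpoint of device-related complications as "Incidence of complications related to the device as judged by the Principal Investigator".

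Section 7.8 states: "This is an open-label study. Blinding is not utilized". Section 10.5.1 makes causality a field that the site completes on the adverse event form. Section 10.2 sets four causality levels, from not related to definite, and has the sponsor and the Principal Investigators together separate device-related from procedure-related serious events. Events that cannot be assessed default to possible. Complications of routine procedures that the protocol does not impose are treated as not related. No section says which levels count as associated or related for the endpoints, and none describes independent or blinded adjudication.

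Section 13.10 lists "Objective methodology to evaluate endpoints" among the safeguards against bias. Sections 3 and 3.3 say that the data will support an initial CE mark application.

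**The concern.** An event enters either endpoint only after someone has judged its cause, and everyone named in that process knows which set was used. One named party, the sponsor, makes one of the two products compared. If similar events are attributed differently in the two arms, the reported proportions differ for reasons unrelated to the devices. Randomisation does not protect against this, because the judgement is made after allocation is known.

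The rules leave room for it. Without a stated cut-off, an event graded possible may or may not count. Section 5.2 describes the study procedures as standard of care, yet the plan does not say whether the routine-procedure rule in Section 10.2 reaches the TIPS itself, or an alternative set used after a failure.

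The study is descriptive, so the proportion in each arm is the result that readers will use. When few events are expected, a single judgement can change that proportion materially.

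**Working it through.** **Inputs.** Subjects per arm: 30, 1:1 (Sections 6.6 and 7.7). Complication rate: 3.6%, puncture-related complications with Cook sets (Section 3.2). It is the only complication rate in the documents, and neither safety endpoint has a stated expected rate.

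**The plan's own figure.** The total of 60 is 30 + 30. Section 11.2 calls it empirical and gives no alpha, power or event rate, so there is no calculation to reproduce.

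**Which endpoint the 3.6% can stand for.** Puncture-related complications are close in kind to device-related complications, so the rate is a usable proxy for the secondary endpoint, and most directly for the Cook arm. It is not a rate for the primary composite, which also takes in procedure-associated events. Section 10.4.1 lists encephalopathy, sepsis, liver failure and death among those anticipated. For the composite I therefore use an assumed range of 5% to 20%.

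**Expected count and weight of one event.** Expected events = 30 × p. Share of the expected count carried by one event = 1 / (30 × p). One event is always 1/30 = 3.3 percentage points. Probabilities are exact binomial: P(0) = (1 − p)^30 and P(1) = 30p(1 − p)^29.

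| Rate p | Status | Expected events | One event as share of expected | P(0) | P(exactly 1) |
|---|---|---|---|---|---|
| 3.6% | cited; proxy for secondary only | 1.08 | 93% | 33.3% | 37.3% |
| 5% | assumed | 1.5 | 67% | 21.5% | 33.9% |
| 10% | assumed | 3.0 | 33% | 4.2% | 14.1% |
| 15% | assumed | 4.5 | 22% | 0.8% | 4.0% |
| 20% | assumed | 6.0 | 17% | 0.1% | 0.9% |

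At 3.6%, an arm has zero or one event with probability 33.3% + 37.3% = 70.6%. Given at least one event, it is the only one with probability 37.3 / (100 − 33.3) = 55.9%.

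**What one reclassification does to the report.** Moving an arm from 1/30 to 0/30 changes 3.3% (Clopper-Pearson 95% interval 0.08% to 17.2%) to 0% (0% to 11.6%). It decides no test: Fisher's exact test gives p = 1.00 for 0 against 1 and for 1 against 2 of 30, and p = 0.49 for 0 against 2.

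**Which moves matter for which endpoint.** Shifting an event from device to procedure removes it from the secondary endpoint but leaves it in the primary, which accepts either cause. Only a finding of not related to both removes it from the primary.

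**Is an attribution-free count feasible?** Section 10.5.1 collects adverse events for all subjects, with severity, seriousness, causality and outcome. Section 6.4.3 records hospital and ICU days. Two gaps remain:

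- Section 6.4.1 follows treatment failures through discharge, while Section 6.7 follows enrolled subjects for 30 days.
- The stepped-up-care criterion in Section 6.4.2 is not a listed adverse event item in Section 10.5.1, and it differs from the serious adverse event definition in Section 10.1.2.

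**The case against.** The strongest reply is that little turns on this. No hypothesis is tested, comparisons are exploratory, and one moved event decides no test. Section 10.2 gives structured causality criteria and sends unassessable events to possible rather than to not related. Overall safety already uses every attempted procedure (Section 11.3.3).

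Part of this stands: the consequence lies in the reported proportions, not in a test result. But those proportions are meant to support a CE mark application. The default to possible protects the endpoints only if possible counts as related, which the plan does not say. Section 11.3.3 also restricts device-specific post-operation safety to procedures that succeeded with the study device alone, so the wider safety set does not cover that assessment.

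Three stronger readings are tempting and are not supported:

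- A reader might infer that the unblinded operator decides both endpoints. Only the secondary endpoint names the Principal Investigator. Section 7.4 has potential subjects contacted "by the treating physician (i.e., the PI) or" site staff, which equates the two roles, but Section 1.3 says: "Any other physicians involved in the study will be documented and referred to as a Sub-Investigator". The person who attributes an event need not be the operator. The sponsor's share under Section 10.2 means that serious events are not one person's call, though it adds no independence.
- A reader might infer that one judgement can erase the expected rate of the primary endpoint. The 3.6% does not describe that composite. At an assumed 10% or 20%, one event is a third or a sixth of the expected count.
- A reader might infer that analysis alone removes the bias. Detection, reporting, seriousness and decisions to escalate care or extend a stay remain unblinded site judgements.

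**Conclusion.** The point holds in this form: both safety endpoints are conditional on attribution, allocation is known to those who attribute, no independent assessor is described, and the causality levels that count are not defined. The claim of objective endpoint evaluation in Section 13.10 does not hold for these two endpoints.

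For the secondary endpoint, with 3.6% as a proxy, one reclassified event is 3.3 points and about 93% of the 1.08 events expected in an arm. For the primary composite, the weight of one event is 67% to 17% of the expected count at assumed rates of 5% to 20%. The documents cannot narrow that range.

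The documents show an opening for arm-dependent attribution. They do not show that it has occurred or in which direction it would run. The change should be made, but nothing here invalidates the design.

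**What to change.** Keep both attributed endpoints and state that possible, probable and definite count as related in them. Say whether the routine-procedure rule in Section 10.2 applies to the TIPS itself.

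Add two tables by randomised arm, in all subjects with an attempted procedure:

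- major complications, defined by consequence as in Section 6.4.2, regardless of attributed cause;
- the ten event types that Section 10.4.2 introduces with "Adverse events related to the use of the Scorpion set or Cook Transjugular Liver Access set may include the following", regardless of attribution.

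Reconcile Sections 6.4.1 and 6.7 on follow-up after treatment failure, so that the count covers the same window in every subject.

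The cost is two tables, a few sentences of definition, the follow-up reconciliation and possibly one eCRF item for an unplanned step-up in care. No added subjects or assessor are needed. The downside is that events from underlying liver disease enter the all-cause count. They are balanced between arms only in expectation, so with 30 per arm they add noise and can dilute a device contrast. For that reason the attributed and all-cause counts should be read together.
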